### **Study Design**

BD type I or II patients (n=160), on a depressive or mixed episode, who were on therapeutic doses of any of the commonly utilized mood stabilizing agents (lithium, anticonvulsants, atypical antipsychotics) for at least one month and who were still symptomatic (MADRAS >20) will be enrolled. Patients will be randomly assigned to orally receive one of 4 conditions: aspirin 1000 mg (2 capsules of 500 mg) qam, NAC 1000 mg (2 capsules of 500 mg) bid, combined aspirin and NAC at same doses as given individually or matched placebo, as an add-on medication to their ongoing treatment regimen, for an 16-week double-blind trial. After the first 8 week of the double blind treatment, the responders will keep taking the same study drug, whichever it is. And the non-responders will be re-randomized for one of the other three groups of study drugs they haven't tried yet.

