During the first 8-week trial, patients will be seen at weeks 0, 1, 2, 3, 4, 6 and 8 for clinical assessment and mood ratings. During the continuation trial, they will be seen at weeks 8, 10, 12, 14 and 16. The main outcome measure for the study will be the scores on the Montgomery-Asberg Depression Rating Scale, MADRAS [62]. All patients will also be assessed with the Young Mania Rating Scale, YMRS [63], the Clinical Global Impression-Bipolar version, CGI-BP [64], and the UKU side-effects scale [65]. In all visits, patients will be seen by the study psychiatrist and the research staff will complete mood ratings with the MADRAS, YMRS, CGI-BD, and the UKU side-effects scale.

At baseline (before randomization), week 8 and week 16 blood will be sampled for proinflammatory markers (C-reactive protein, soluble interleukin (IL)-2 receptor, IL-6 and tumor necrosis factor (TNF)-alpha), and oxidative stress

markers (superoxide dismutase activity and catalase activity, serum thiobarbituric acid reactive substances (TBARS)), which have been reported to be elevated in BD patients [34] [33] [35]. These blood samples will be stored for possible future research on biomarkers or future genetic studies for up to 20 years, for use in pharmacogenetic research during this 20 year timeframe. The samples will be stored at the Wet Lab, in a double locked -80 degrees freezer, at [REDACTED]

[REDACTED] for future use studying factors of Bipolar Disorder. When (or before) the 20 year period ends, the blood sample will be destroyed.

Patients will complete neuropsychological testing at baseline and Week 16. The testing will include CANTAB, WASI, and WRAT assessments and will take approximately 3-4 hours.

At the screening visit, week 8, and week 16 we will also be testing the Lithium levels in all patients that have been prescribed and currently taking the medication for study purposes. This extra test will be conducted for the safety of the patient and more Lithium level tests can be ordered under the PI's discretion throughout the 16 week trial.

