### **Safety considerations:**

Aspirin is a safe medication for administration to humans and is approved by the FDA as an anti-inflammatory and analgesic agent. The dose proposed for this study is within the safety range as per medication package. Its side-effect profile is overall very favorable and it has met widespread use worldwide over the past decades. The main safety issues relate to the possibility of gastrointestinal complications, which are rare (and will be closely monitored in the weekly or biweekly visits that the study requires), and the propensity to interfere with coagulation and cause consequent bleeding (which will be prevented by excluding any individuals on use of anticoagulants or with active bleeding problems). There were a few case reports and small case series with other non-steroidal anti-inflammatory agents suggesting worsening of depressive symptoms related to treatment (e.g., indomethacin, ibuprofen, naproxen), but those were uncontrolled reports with individuals who suffered from other medical illnesses (rheumatologic diseases) [66] [67]. For our proposed trial, because some patients may be on lithium at the time they start on aspirin, we will exclude individuals with pre-existing cardiac and kidney disease. For patients on lithium, we will carefully monitor their serum lithium levels every two weeks during the course of the trial. Therefore, at the doses that are being proposed we do not anticipate any significant problems related to safety of the proposed intervention.

NAC is a safe compound that is commonly available and utilized over-the-counter. In a recent study [54] the tolerability was excellent and main side effects included changes in energy level, headaches, heartburn and joint pain.

Blood Draws: When the blood is drawn, there may be some minimal discomfort and/or bruising. Infection, excess bleeding, clotting, or fainting is also possible, although unlikely. All usual precautions will be taken to prevent these possibilities and these risks will be minimized by using trained staff to perform the blood draws.

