### **General Data Analytic Strategies**

All statistical analyses will use SAS v. 9.2 (SAS Institute Inc., Cary, N.C.). Preliminary data analyses inspecting group differences on demographic and baseline variables will evaluate posterior distributions for differences in proportions and means, as well as for correlations between baseline variables and specified outcomes. Baseline or demographic variables for which the posterior distribution indicates there is > 99% chance of a difference across groups, and for which there is a > 99% chance of a non-zero correlation with outcomes, will be defined as potential confounders and will result in two sets of analyses: one in which the relevant variable is included as a covariate and one in which it is not. This will permit determination of the degree to which any group differences might confound conclusions regarding treatment.

Evaluation of the primary outcome, proportion of patients demonstrating > 50% decrease in depression scores on the MADRS, as a function of treatment will use a beta-binomial model and contingency tables with chi-square testing for Bayesian and Frequentist approaches respectively. Additional analyses will use the generalized linear modeling. Count, dichotomous and continuous Bayesian analyses will be conducted using Poisson (Proc GENMOD; SAS 9.2), logistic (Proc GENMOD; SAS 9.2), linear (Proc GENMOD; SAS 9.2) regression respectively. Distributional assumptions will be evaluated via inspection of residual plots and, where possible, by formal statistical tests. Violation of assumptions will be addressed, depending upon statistical technique, through the use of transformations, robust methods, and stratification.

Unless otherwise indicated in the data analytic plan, priors will be specified as neutral and diffuse. The beta-binomial model will use a  $\sim\text{Beta}(1,1)$  prior distribution. For linear, Poisson, and logistic regression, priors will take the form  $\sim\text{N}(0, 1 \times 10^6)$  in the linear, log, and log(odds) scales respectively. Convergence of Bayesian analyses on the posterior distributions via Monte-Carlo Markov chain (MCMC) will be assessed via graphical (Trace Plot, Autocorrelation Plot) and quantitative (Geweke Diagnostics, Gelman-Rubin Diagnostics, and Heidelberger-Welsh Diagnostics) evidence. Evaluation of posterior distributions will permit statements regarding the probability that effects of varying magnitudes exist, given the data.

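### The plan does not keep the MADRS rater away from side-effect information, so rater blinding on the primary outcome is an unprotected risk

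*Combined protocol and SAP*

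**What the plan says.** Under Study procedures, "The main outcome measure for the study will be the scores on the Montgomery-Asberg Depression Rating Scale". The analysis section (General Data Analytic Strategies) turns this into a binary primary outcome, the "proportion of patients demonstrating > 50% decrease in depression scores on the MADRS".

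In the first treatment period "patients will be seen at weeks 0, 1, 2, 3, 4, 6 and 8 for clinical assessment and mood ratings". On who does what, Study procedures says that "In all visits, patients will be seen by the study psychiatrist" and that "the research staff will complete mood ratings with the MADRAS, YMRS, CGI-BD, and the UKU side-effects scale". No scale is assigned to the psychiatrist.

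Blinding is described at the level of the capsules. Study Design lists the single drugs, "combined aspirin and NAC at same doses as given individually or matched placebo", in a double-blind trial. I found no text on separate efficacy and safety raters, the order of the scales, withholding side-effect forms from the mood rater, or checking whether the blind held.

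Safety considerations names the effects that might give a hint. For aspirin, "The main safety issues relate to the possibility of gastrointestinal complications", which the same sentence calls rare, and a bleeding tendency, to be handled by exclusions. For NAC, tolerability in a previous study is called excellent, and the "main side effects included changes in energy level, headaches, heartburn and joint pain".

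**The concern.** The MADRS is scored by an interviewer's judgement. Someone who also records side effects can form a view on whether a patient is on active drug, and that view can colour the score. A correct guess of the exact arm is not needed. Suspecting active drug rather than placebo is enough, and three of the four arms are active.

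The order of scales on the day does not remove the problem. By the week-8 MADRS, the UKU has been due at weeks 0, 1, 2, 3, 4 and 6. If week 0 is the pre-treatment baseline, five of those are on treatment.

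The outcome is a threshold on the percentage fall in score, so a small lean can move patients across it. The same ratings feed three places: the active-versus-placebo response comparison, the interim step that asks whether any treatment differs decisively from placebo, and the week-8 responder classification that decides who is re-randomised.

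**Working it through.** **Inputs from the documents.** Placebo response 25% (Simulation Study). An average of 60 patients each in the retained treatment and placebo, alpha 0.05, and stated power for 0.25 versus 0.50 of 81.80% at 60 per group and 65% at 40 per group (Statistical analyses, power paragraph).

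**Assumptions not in the documents.** SD of the week-8 MADRS 8 to 10 points; a normal distribution with a fixed response cut-off; the size of any rater lean; the share of patients it touches.

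**Step 1: reproduce the plan's figures.** For n per group, with a and b responders, z = [(b − a)/n] / √[2p̄(1 − p̄)/n], where p̄ = (a + b)/(2n). Summing the binomial probabilities of all outcomes with |z| > 1.96 gives:
- 0.25 versus 0.50, n = 60: 81.8% (plan 81.80%)
- 0.25 versus 0.50, n = 40: 64.7% (plan 65%)
- 0.25 versus 0.25, n = 60: 5.2%, the false-positive rate without any lean

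The plan's figures therefore correspond to a two-sided chi-square test without continuity correction.

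**Step 2: a lean averaged over all active patients, with no true effect.** A lean of L points lowers rated scores in the active arm, so its response rate becomes Φ(z₀ + L/SD), with z₀ = Φ⁻¹(0.25) = −0.6745.
- L = 1, SD 8: Φ(−0.6745 + 0.125) = Φ(−0.5495) = 0.291, a rise of 4.1 percentage points
- L = 1, SD 10: Φ(−0.6745 + 0.100) = Φ(−0.5745) = 0.283, a rise of 3.3 percentage points

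**Step 3: a lean confined to some patients.** If only an excess fraction f of active patients over placebo gives a cue, the active response rate is 0.25 + f × [Φ(z₀ + L/SD) − 0.25]. For L = 2, the bracket is 0.336 − 0.25 = 0.086 at SD 8 and 0.318 − 0.25 = 0.068 at SD 10. With f = 0.1 the rise is 0.7-0.9 points; with f = 0.2 it is 1.4-1.7 points.

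**Results at 60 versus 60** (ranges cover SD 10 to SD 8):

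| Lean | Patients affected | Rise in active response (points) | Two-sided false-positive rate |
|---|---|---|---|
| none | none | 0 | 5.2% |
| 0.5 point | all active | 1.6-2.0 | 5.7-6.0% |
| 1 point | all active | 3.3-4.1 | 7.2-8.3% |
| 2 points | 10% excess | 0.7-0.9 | 5.3-5.4% |
| 2 points | 20% excess | 1.4-1.7 | 5.6-5.8% |
| 2 points | 50% excess | 3.4-4.3 | 7.3-8.6% |
| 2 points | all active | 6.8-8.6 | 13.4-18.3% |

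**Step 4: effect on the interim.** The pruning rule first asks whether any treatment differs decisively from placebo, then takes the active arm with the highest posterior probability of benefit. A lean shared by all active arms raises each against placebo, so it bears on the first step. It gives no active arm an advantage over another in the second.

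**The case against.** Four stronger readings are tempting, and the documents support none of them.

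1. A reader might infer that one person takes the side-effect scale and then scores the MADRS. The plan speaks of a staff group, gives no order, and lists the MADRS first and the UKU last. What stands is that the plan allows one person to do both, and that knowledge from earlier visits carries over whatever the order.

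2. A reader might infer that the side effects reveal the arm. The plan calls gastrointestinal complications rare, expects the exclusions to prevent bleeding, and calls NAC tolerability excellent. Headache, heartburn, joint pain and energy change are non-specific, and patients on background psychotropics may report them in any arm, placebo included. They can hint at active drug; nothing shows that they identify it.

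3. A reader might take the 13-18% false-positive rate as the likely size. It requires a 2-point lean averaged over every active patient with none on placebo. If effects are uncommon or non-specific, only the excess of cued patients over placebo counts, and the inflation is far smaller.

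4. A reader might infer that the interim would be steered to a particular arm. A lean common to the active arms does not do that. A lean that differed between arms could, but the documents offer no basis for assuming one.

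It is also fair to say that matched capsules and a double-blind design are in place, and that moving the UKU will not stop patients from mentioning side effects in the mood interview. These points reduce the expected size. They do not fill the gap, because matching the capsules does not keep the rater from what patients report.

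**Conclusion.** The point holds as an unprotected risk to rater blinding. It is neither a contradiction in the plan nor a demonstrated bias. The joint assignment of the MADRS and UKU to one staff group at all visits is explicit, and no safeguard is written anywhere.

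Its size cannot be settled from the documents. It could be close to negligible (5.3-5.8% against 5.2%) if cues are confined to a small excess of active patients, or moderate (7.2-8.3%) if the lean averages 1 point over all of them. Both ranges rest on the assumed SD, lean and share of patients affected; only the placebo rate and group size come from the plan. A lean would touch the active-versus-placebo comparison, the decisive-difference step and the week-8 responder classification, but not the choice among active arms if it is common to them. Because the safeguard costs little, it is worth adding even though the harm may be small.

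**What to change.** In Study procedures, split the assessments between roles already present at each visit. The study psychiatrist completes the UKU and records adverse events. The research staff complete the MADRS, YMRS and CGI-BP and have no access to the UKU form or the adverse-event notes, from the current or earlier visits.

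The cost is some extra psychiatrist time per visit; no staff, visits or patients are added. The split is not complete protection, since patients may still volunteer side effects during the mood interview.

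Optionally, have the MADRS rater record a guess of the arm at week 8, so that the state of the blind can be reported with the results. This adds one short item for the rater.

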### **Safety considerations:**

Aspirin is a safe medication for administration to humans and is approved by the FDA as an anti-inflammatory and analgesic agent. The dose proposed for this study is within the safety range as per medication package. Its side-effect profile is overall very favorable and it has met widespread use worldwide over the past decades. The main safety issues relate to the possibility of gastrointestinal complications, which are rare (and will be closely monitored in the weekly or biweekly visits that the study requires), and the propensity to interfere with coagulation and cause consequent bleeding (which will be prevented by excluding any individuals on use of anticoagulants or with active bleeding problems). There were a few case reports and small case series with other non-steroidal anti-inflammatory agents suggesting worsening of depressive symptoms related to treatment (e.g., indomethacin, ibuprofen, naproxen), but those were uncontrolled reports with individuals who suffered from other medical illnesses (rheumatologic diseases) [66] [67]. For our proposed trial, because some patients may be on lithium at the time they start on aspirin, we will exclude individuals with pre-existing cardiac and kidney disease. For patients on lithium, we will carefully monitor their serum lithium levels every two weeks during the course of the trial. Therefore, at the doses that are being proposed we do not anticipate any significant problems related to safety of the proposed intervention.

NAC is a safe compound that is commonly available and utilized over-the-counter. In a recent study [54] the tolerability was excellent and main side effects included changes in energy level, headaches, heartburn and joint pain.

Blood Draws: When the blood is drawn, there may be some minimal discomfort and/or bruising. Infection, excess bleeding, clotting, or fainting is also possible, although unlikely. All usual precautions will be taken to prevent these possibilities and these risks will be minimized by using trained staff to perform the blood draws.

Women Able to Become Pregnant: Participation in this study may involve risks to an embryo, fetus, or unborn child. If the subject is a female and able to become pregnant, a urine pregnancy test will be performed which must be negative prior to enrolling into the study, and the subject must agree not to become pregnant during the study. Urine pregnancy tests will be performed at Screening visit and week 8. The study staff will review adequate birth control methods with the subject and will remind her that she should not become pregnant during the study. Appropriate methods of birth control include: hormonal contraceptives (such as birth control pills, patches, and implants), barrier methods (such as a condom and diaphragms and spermicidal foam or jelly, surgical (hysterectomy or tubal ligation) or intrauterine device (IUD). The subject will be instructed to notify the study doctor immediately if there is a chance that she has become pregnant.

Also, if the subject is breast-feeding an infant or plan on breast-feeding an infant, she must notify the study doctor. It is not known if this drug is excreted in human milk; therefore, breast-feeding is not permitted during the study.

**Breach of Confidentiality:** Every effort will be made to protect the subject identity and information during the study. All lab work and scan reports will be de-identified and the medical records will be protected. However, there is a small chance that the subject information may be viewed by someone that is not involved in the research study.

The study drug must be taken only by the person for whom it has been prescribed, and it must be kept out of the reach of children or persons of limited capacity to read or understand.

By sharing your sample with the study doctor, there is a risk of the possible loss of the subject privacy. Although no identifiable (name, address, etc.) information will be shared with others outside of this research project. The clinical information obtained from subjects will be part of their medical records and maintained at UT Center of Excellence on Mood Disorders, in the Department of Psychiatry at UTHSC-H, in facilities with adequate safeguards for the protection of confidentiality. The research data will be collected and recorded using only arbitrary code numbers for identification, in order to safeguard the confidentiality. All data will be kept in a secure area. Only the members of the UT Center of Excellence on Mood Disorders research group, who will get approval from CPHS, will have access to the data files, or to the master list for the codes. For publications purposes, the patients will be designated only by their assigned codes.

These blood samples, for use in pharmacogenetic research during this 15 year timeframe, samples will be stored at the Wet Lab, in a double locked -80 degrees freezer, at [REDACTED]

The possibility exists that the subject information may be taken and used for reasons outside of this project. The United States' Genetic Information Nondiscrimination, Act (GINA) of 2008, does not allow for employers or health insurance companies to discriminate against the research subject based on his/her genetic information. This means that health insurance companies or employers are NOT ALLOWED BY LAW to ask or use any of the subject genetic information (DNA, RNA, etc.) gained through testing to make decisions that affect the subject or hisher family's health coverage or income in a negative way.

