If patients qualify for the study initially based on SCID-I interview, physical examination, and routine labs (CBC, liver functions tests, electrolytes, kidney function tests, thyroid function tests, HIV testing, and urinalyses), but are not currently taking an approved psychotropic medication or combinations they are eligible to participate in a lead-in phase. This phase would be starting at their screening visit and last approximately 6 to 8 weeks depending on the patient's mood. During this lead-in phase, either the PI or Co-PI will evaluate the patient and prescribe either Lithium or Depakote. The patient will be monitored during this treatment phase by the PI or Co-PI and will return after two weeks for an evaluation. The evaluation will include CSSR-S and adverse effects. If the patient is prescribed lithium, their lithium levels will be tested. The patient will continue to follow up every two weeks. At the 4 week visit, the patient will also come in for evaluation (CSSR-S and adverse effects). At the 6 week visit, the patient will be re-evaluated for the double-blind study trial. If the patient has been on an adequate dose of the psychotropic medication for at least 4 weeks and score greater than 20 on the Montgomery-Asberg Depression Rating Scale (MADRS), then they will be enrolled. If they do not meet inclusion criteria at the week 6 lead-in phase visit, they will return at Week 8 and be re-evaluated. PI and Co-PI will continue to prescribe the psychotropic medication throughout the lead-in phase (up to 8 weeks) and through the trial (up to 16 weeks).

During the lead-in phase participants will not be compensated. They will receive a voucher for their parking for each visit. They will be responsible for filling and paying for all prescriptions in both the lead-in phase and through the trial (up to 16 weeks).

Upon completion of the first 8-week double-blind trial, patients who responded to the active medication will continued on the same study drug for an additional 8 week double-blind treatment. The non-responders to one of the study drugs will be re-randomized for one of the other three groups of study not received and will remain in treatment for an additional 8 week double-blind treatment. Treatment response will be defined as improvement in the **MADRS scores of at least 50%**.

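### The serum lithium schedule for the 16-week trial is unreconciled: two-weekly in Safety considerations, but scheduled only at screening, week 8 and week 16 in Study procedures

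*Combined protocol and SAP*

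**What the plan says.** Two sections of the Combined protocol and SAP set lithium testing for the treatment period.

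- **Safety considerations** notes that some patients may already be on lithium when aspirin is added. It gives two safeguards. Patients with pre-existing cardiac or kidney disease are excluded, and for patients on lithium "we will carefully monitor their serum lithium levels every two weeks during the course of the trial". The next sentence draws the conclusion that no significant safety problem is expected at the proposed doses.
- **Study procedures** sets a different schedule: "At the screening visit, week 8, and week 16 we will also be testing the Lithium levels in all patients" who are prescribed and taking lithium. It adds that "This extra test will be conducted for the safety of the patient" and that "more Lithium level tests can be ordered under the PI's discretion throughout the 16 week trial".

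Study procedures also fixes the visits. "During the first 8-week trial, patients will be seen at weeks 0, 1, 2, 3, 4, 6 and 8", and "During the continuation trial, they will be seen at weeks 8, 10, 12, 14 and 16". It adds: "In all visits, patients will be seen by the study psychiatrist".

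The lead-in phase, also in Study procedures, has its own lithium test: "If the patient is prescribed lithium, their lithium levels will be tested". That phase comes before enrolment in the double-blind trial.

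**The concern.** The same test at the same weeks is a commitment in one section, while the other does not schedule it and leaves additional tests to judgement. Study procedures is where site staff would look for what to do at each visit, and no two-weekly on-treatment level appears there. The document does not say which schedule governs.

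The stake is patient safety. The protocol itself raises lithium combined with aspirin as a concern and answers it partly with frequent levels. If the sparser schedule is the one carried out, much of that support is lost. Three features of the design make discretionary testing a weak substitute:

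- The trial is double-blind, so the investigator should not know which lithium patients are taking aspirin and cannot direct extra tests to them.
- Week 8 non-responders are re-randomized to a group they have not received. For a placebo or NAC non-responder, two of the three remaining groups contain aspirin (before any arm is dropped), so aspirin can start halfway through the trial.
- Kidney function and electrolytes are listed among the entry laboratory tests and are not scheduled again on treatment. The lithium level is therefore the only scheduled on-treatment laboratory check on this concern.

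**Working it through.** The plan gives no count of its own to reproduce. The check lists the levels each section requires and compares them with the visit schedule.

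**Inputs**
- Safety considerations: every two weeks during the trial, for patients on lithium.
- Study procedures: screening, week 8 and week 16, with more tests permitted at discretion.
- Study procedures, visits: weeks 0, 1, 2, 3, 4, 6, 8, then 8, 10, 12, 14, 16.
- Duration: 16 weeks, with possible aspirin starts at week 0 and at the week 8 re-randomization.

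**Counting rule.** Only levels after week 0 are counted, and two-weekly is counted from week 0. The week 8 sample is taken as drawn before any re-randomized drug is started.

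| | Safety considerations | Study procedures alone |
|---|---|---|
| Required on-treatment levels | weeks 2, 4, 6, 8, 10, 12, 14, 16: 16 / 2 = 8 | weeks 8, 16: 2 |
| Longest gap between required levels on treatment | 2 weeks | 16 − 8 = 8 weeks |
| First required level after aspirin starts at week 0 | week 2: 2 − 0 = 2 weeks | week 8: 8 − 0 = 8 weeks |
| First required level after aspirin starts at week 8 | week 10: 10 − 8 = 2 weeks | week 16: 16 − 8 = 8 weeks |
| Required levels after aspirin starts at week 8 | weeks 10, 12, 14, 16: 4 | week 16: 1 |

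**Difference.** 8 − 2 = 6 levels, at weeks 2, 4, 6, 10, 12 and 14, are required by Safety considerations but not by Study procedures. For a week 8 aspirin start, the single required later level under Study procedures falls when treatment ends.

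**Feasibility.** All eight two-weekly points coincide with an existing visit, so the two-weekly schedule needs 0 new visits.

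**Can the wording be reconciled?**
1. *The week 8 and week 16 tests come on top of two-weekly ones.* The words also and extra allow this reading. But weeks 8 and 16 already lie on the two-week grid, so only the screening test would be additional. Leaving further tests to discretion also fits poorly with a mandatory two-weekly schedule.
2. *The phrase about study purposes limits the sparser schedule to lithium started in the lead-in.* The text refers to all patients, and it tests at screening, when lead-in patients have not yet begun lithium. Even on this reading, the lead-in patients have two schedules.
3. *The lead-in test settles it.* That test precedes enrolment and says nothing about the 16 weeks of treatment.

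**The case against.** The strongest case is that this is an incomplete procedures section and not two incompatible rules. Study procedures never says that levels are taken only at three times. It permits more, and permission to order more tests does not cancel a requirement stated elsewhere in the same protocol. A site that samples every two weeks complies with both sections. The 2-against-8 comparison is a worst case in which the Safety considerations commitment is ignored. The scope is also arguable: if the sparser schedule covers only lithium prescribed in the lead-in, patients who arrive on their own lithium fall under Safety considerations alone. Finally, there are real mitigations: the cardiac and kidney exclusions, kidney function tests at entry, psychiatrist review and a side-effects scale at every visit, an investigator who keeps prescribing for lead-in patients, and discretionary testing.

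Much of this stands. A reader might infer that Study procedures makes every other lithium test optional, or that the two sections cannot both be followed. The documents do not support either inference: the text says only that more tests can be ordered, and two-weekly sampling satisfies both. The counts must therefore carry the condition that staff follow Study procedures alone.

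The objection does not remove the problem. The section that directs visits does not list six levels on which the safety argument relies, and none of the mitigations makes a level mandatory. The narrower scope reading is weakened by the screening test and would still leave two schedules for lead-in patients.

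**Conclusion.** The plan is wrong as written: the lithium schedule for the 16 weeks is unreconciled, and the safety conclusion rests partly on the denser version. On the condition that staff follow Study procedures alone, 6 of the 8 two-weekly levels are not required, and the wait for a required level after starting aspirin is 8 weeks instead of 2, at either possible start. Slight ambiguity remains from the description of the scheduled test as extra.

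A reader might go further and infer that lithium patients will go unmonitored or come to harm. The documents do not support that. They give neither the share of patients on lithium nor the size of any effect of aspirin on lithium levels, so no patient count or harm estimate can be made. There is no effect on sample size, power or type I error.

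**What to change.** Amend Study procedures to require serum lithium, for every patient on lithium, at screening and at the existing visits in weeks 2, 4, 6, 8, 10, 12, 14 and 16, with further tests at the investigator's discretion.

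If the sparser schedule is what is intended, correct the two-weekly statement in Safety considerations and rewrite the safety conclusion that follows it so that it no longer relies on two-weekly levels.

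The cost of the main change is protocol wording and six more blood draws per lithium patient than Study procedures now requires (weeks 2, 4, 6, 10, 12 and 14). All fall at existing visits, and Safety considerations already promises them. The lead-in lithium test needs no change for this purpose.
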